If symptoms resolve within a single study visit and the investigator determines the symptoms were not an occurrence of progressive or severe hypersensitivity, anaphylaxis, or anaphylactoid reactions then administration of the drug may continue according to the algorithm provided above, and at the discretion of the Investigator and Medical Director.

Premedication

Premedication for subsequent PRX-102 infusions may be considered at the discretion of the investigator and Medical Director for subjects experiencing early clinical signs of hypersensitivity or rash/urticaria that responds promptly to oral antihistamine administration (see also Appendix 2 for adjustment of infusion rate). The premedication will be administered according to the following steps as needed to prevent progressive hypersensitivity:

1. Antihistamine (H1 blocker: diphenhydramine, hydroxyzine, cetirizine, loratadine, desloratidine) at a standard dose 12 hours and 2 hours before the start of the infusion.
2. H1 blocker plus H2 blocker (ranitidine, cimetidine, famotidine) at standard doses 12 hours and 2 hours before the start of the infusion.
3. H1 blocker plus H2 blocker plus prednisone up to 50 mg administered 12 hours and 2 hours before the start of the infusion.

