9.1.3. Treatment-Emergent Adverse Events (TEAE)

Number and percent of patients with at least one TEAE as well as the number of TEAE in the following categories will be summarized overall and by the subgroups presented in Section 7.4:

- Any TEAE
- Treatment non-related (unlikely, not-related) TEAE
- Treatment related (defined as possibly, probably or definitely related) TEAE
- Mild or moderate TEAE
- Treatment related mild or moderate TEAE
- Severe TEAE

- Treatment related severe TEAE
- Serious TEAEs
- Treatment related serious TEAE
- TEAE leading to withdrawal
- Treatment related TEAE leading to withdrawal
- TEAE leading to death
- Treatment related TEAE related to death.

These tables above will be repeated for the number and percentage of patients with at least one injection site reaction TEAE.

Summary tables will be presented for the frequency of any TEAEs by the MedDRA SOC and PT by overall and by the subgroups presented in Section 7.4; by the MedDRA SOC and PT and severity of TEAE; by MedDRA SOC and PT, and the relationship of TEAEs to study drug.

Summary tables will be presented for the frequency of serious TEAEs by the MedDRA SOC and PT for overall and by gender and by the MedDRA SOC and PT and relationship to study drug.

In the summaries of severity and relationship to study drug, the most extreme outcome (highest severity and closest relationship to study drug) will be used for those subjects who experience the same TEAE (per preferred term) on more than one occasion.

Missing values associated with TEAEs will be treated as missing except for causality, intensity, and outcome of a TEAE, at which occurrence a “worst case” approach will be taken in the analysis. Thus

- If causality is missing, the TEAE will be regarded as related to pegunigalsidase alfa
- If the intensity is missing, the intensity of the AE will be regarded as severe
- If the outcome is missing and the stop date is not provided, the outcome is regarded as “ongoing”.
- If the seriousness is missing, all efforts should be made prior to database lock to make sure that this information is available, if still missing, the worst-case scenario is assumed.

If there were any TEAEs leading to withdrawal or death, these cases will be presented by patient.

Listing of TEAE will include also the TEAE onset and end date and also relative to first pegunigalsidase alfa infusion.

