9.1.4. Time-categories of TEAE

TEAE will be classified by time of occurrence in relationship to the infusion into one of the following 3 categories:

- Occurring during the infusion or within 2 hours after the completion of the infusion
- Occurring between 2 hours after the completion of the infusion and 24 hours after the completion of the infusion
- Occurring at least 24 hours after the completion of the infusion

A summary of TEAE (number and percentage of subjects with TEAE and number of TEAEs) by the MedDRA SOC and PT and by the three time-categories will be presented

The following rules, including imputation convention when there is missing date/time of TEAE onset and/or infusion, will be applied:

Category #1. TEAE occurring during the infusion or within 2 hours after the completion of infusion.

A TEAE will be classified into this category if date and time are available for both the TEAE and the last infusion and the TEAE onset during the infusion or the time from the stop of infusion to time of TEAE onset < 2 hours.

Category #2. TEAE occurring between 2 hours and 24 hours after the completion of infusion.

A TEAE will be classified into this category if

(1) date and time available for both TEAE and the last infusion and the time from the stop of infusion to time of TEAE onset \geq 2 hours but < 24 hours, or

(2) the time of TEAE onset is not available, but the date of TEAE onset is the same day of the last infusion.

Category #3. TEAE occurring at least 24 hours after the completion of infusion.

A TEAE will be classified into this category if

- (1) the date and time available for both TEAE and the last infusion and the time from the stop of infusion to time of TEAE onset \geq 24 hours, or
- (2) the time of TEAE onset is not available, but the onset date is after the date of last infusion, or
- (3) TEAE onset date is incomplete, or
- (4) the date and time of last infusion cannot be determined.

Per the Drug Administration CRF, there are three options: (1). “During the infusion”, (2). “Within 2 hours after the infusion”, and (3). “Up to 24 hours after the infusion” to be selected if the answer is Yes to the question “Did the patient experience an Adverse Event

during or after the infusion?”. The specific adverse event and a date and/or time (not specified, but in the context, the date/time should be the onset date/time of the adverse event) were collected in a text field.

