The information will be used to derive the variables necessary to associate with the adverse events entered in the Adverse Events CRF. The record with a selection of the three options but without specific adverse event or date of onset, or vice versa, will not be considered in determination of the time category.

For those adverse events reported on the Drug Administration CRF, matched by the original term of adverse event and onset date/time on the Adverse Events CRF, the time category will be assigned as follows, which overrides the category assigned by the above rules.

Category #1. TEAE occurring during the infusion or within 2 hours after the completion of infusion.

The TEAE will be classified into this category if the selection of the three options is either (1). During the infusion, or (2). Within 2 hours after the infusion.

Category #2. TEAE occurring between 2 hours and 24 hours after the completion of infusion.

The TEAE will be classified into this category if the selection of the three options is (3). Up to 24 hours after the infusion.

Category #3. TEAE occurring at least 24 hours after the completion of infusion.

Not applicable.

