9.1.5. Infusion Related Reactions (IRR)

The IRRs are those treatment emergent adverse events (TEAE) which occurred during the infusion or within 2 hours after the completion of the infusion and the causality of the adverse events are determined to be definitely, probably, or possibly related, based on the the site reports in the eCRF.

Injection site reactions which are not considered IRR are excluded from the summary of IRRs, and will be identified based on their SOC and PT, as listed in the following table:

MedDRA SOC	MedDRA Preferred Term
General disorders and administration site conditions	Infusion site discomfort
	Injection site discomfort
	Infusion site pain
	Injection site pain
	Infusion site hematoma
	Injection site hematoma
Injury poisoning and procedural complications	Contusion
	Procedural site reaction
	Procedural pain
Vascular disorders	Vein rupture

The number and percentage of IRRs in the following categories will be summarized for overall, and by gender, FD Classification, and Treatment Emergent pegunigalsidase alfa ADA. The percentage will be based on the total number of IRRs of the population or subset. In addition, the number and percentage of IRR will be summarized by administration location (Home/Site). The summary will include the

following categories:

- Overall number of IRR (used to calculate the percentage),
- Mild or Moderate IRR,
- Severe IRRs,
- Very Severe IRRs,
- Serious IRR.
- IRR that lead to study discontinuation
- IRR that lead to death

Number and percentage of patients with IRRs by MedDRA SOC and PT will be summarized for overall, and by gender, FD Classification, and Treatment Emergent ADA. The number and percentage of patients with IRRs by MedDRA SOC and PT and severity will be summarized for overall.

Number of IRRs by MedDRA SOC and PT will be summarized for overall, and by gender, FD Classification, and Treatment Emergent pegunigalsidase alfa ADA. The number of IRRs by MedDRA SOC and PT and severity will be summarized as well for overall.

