14.2.2.10.1	Mainz Severity Score Index (MSSI) for Overall and by Gender	EP, PP
14.2.2.10.2	Mainz Severity Score Index (MSSI) - Shift from Baseline for Overall	EP, PP
14.2.2.11.1	Usage of Pain Medications for Overall and by Gender	EP, PP
14.2.2.11.2	Usage of Various Pain Medications for Overall and by Gender	EP, PP
14.2.2.11.3	Pain Medication Use – Shift from Baseline to Last Visit for Overall and by Gender	EP, PP
14.2.2.11.4	Number of Pain Medication Use – Shift from Baseline to Last Visit for Overall and by Gender	EP, PP
14.2.2.12.1	Number of Subjects with Fabry Clinical Events for Overall and by Gender	EP, PP
14.2.2.12	Number of Subjects with Fabry Clinical Events by Baseline FD Classification and Treatment Emergent ADA	EP, PP

Safety – Adverse Events:

Number	Title	Population
14.3.1.1.1	Number of Subjects with Treatment-Emergent Adverse Events for Overall and by Gender	Safety
14.3.1.1.2	Number of Subjects with Treatment-Emergent Adverse Events by Baseline FD Classification and Treatment Emergent ADA	Safety
14.3.1.2.1	Number of Treatment-Emergent Adverse Events for Overall and by Gender	Safety
14.3.1.2.2	Number of Treatment-Emergent Adverse Events by Baseline FD Classification and Treatment Emergent ADA	Safety
14.3.1.3.1	Number of Subjects with TEAE by MedDRA System Organ Class / Preferred Term for Overall and by Gender	Safety
14.3.1.3.2	Number of Subjects with TEAE by MedDRA System Organ Class / Preferred Term by Baseline FD Classification and Treatment Emergent ADA	Safety
14.3.1.4	Number of Subjects with TEAE by MedDRA System Organ Class / Preferred Term and Severity for Overall	Safety
14.3.1.5	Number of Subjects with TEAE by MedDRA System Organ Class / Preferred Term and Relationship to Study Drug for Overall	Safety
14.3.1.6	Number of Subjects with Pre-Treatment AE by MedDRA System Organ Class / Preferred Term for Overall and by Gender	Safety
14.3.1.7	Number of Subjects with TEAE by MedDRA System Organ Class / Preferred Term by Time Categories for Overall	Safety
14.3.1.8	Number of TEAEs by MedDRA System Organ Class / Preferred Term by Time Categories for Overall	Safety
14.3.1.9.1	Number of IRRs for Overall, by Gender and Location of Administration	Safety
14.3.1.9.2	Number of IRRs by Baseline FD Classification and Treatment Emergent ADA	Safety
14.3.1.10.1	Number of IRRs by MedDRA System Organ Class / Preferred Term for Overall and by Gender	Safety

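### A related infusion-day event with no onset time is placed outside the 2-hour window by default, which can only lower the count of infusion-related reactions

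*SAP*

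**What the plan says.** **Definition.** SAP 9.1.5 defines an IRR as a treatment-emergent event that "occurred during the infusion or within 2 hours after the completion of the infusion" and is judged possibly, probably or definitely related. A listed set of injection site reactions is excluded.

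**Time categories.** SAP 9.1.4 sorts all TEAEs into three categories. Category 1 is the same window as the IRR definition. It requires date and time for both the event and the last infusion, and then that "the TEAE onset during the infusion or the time from the stop of infusion to time of TEAE onset < 2 hours". Category 2 covers 2 to 24 hours. It also takes any event for which "the time of TEAE onset is not available, but the date of TEAE onset is the same day of the last infusion".

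**Override.** A site's tick-box answer on the Drug Administration CRF replaces the derived category, but only for events "matched by the original term of adverse event and onset date/time on the Adverse Events CRF". Incomplete records are set aside: "The record with a selection of the three options but without specific adverse event or date of onset, or vice versa, will not be considered".

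**Other missing TEAE fields.** SAP 9.1.3 takes the worst case. For example, "If causality is missing, the TEAE will be regarded as related to pegunigalsidase alfa". Missing intensity is read as severe, and missing seriousness is resolved to the worst case if it cannot be retrieved. Onset time is not among these fields; its handling is in 9.1.4.

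**The concern.** IRR status depends on two facts, relatedness and timing. When relatedness is missing, the plan assumes the adverse answer. When the clock time is missing on an infusion day, it assumes the favourable one. An event with neither causality nor onset time recorded would be made related by one rule and then taken out of the IRR count by the other.

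The error can run in one direction only, because the derived rules never place an untimed event in Category 1. Safety is the primary objective, and Protocol 6.2 gives possible differences in hypersensitivity and premedication need between the two enzymes as a design consideration. The IRR tables (14.3.1.9 to 14.3.1.13) are where a reader would look for that.

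**Working it through.** The plan states no figure on this point, so the check traces the rules and then sizes one displaced patient.

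**Step 1. Trace a related TEAE dated on an infusion day** (not one of the excluded injection site reactions), using SAP 9.1.4 and 9.1.5.

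| Onset time | Drug Administration CRF record | Category | IRR? |
|---|---|---|---|
| Known, in the window | No match | 1 | Yes |
| Missing | Matched; first or second tick-box option | 1, by override | Yes |
| Missing | Matched; third option (up to 24 hours) | 2, by override | No |
| Missing | None, or lacks the event or the date | 2, by default | No |
| Missing | Has term and date but no time | Not stated | Depends on whether a date-only match counts |

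The fourth row is the point at issue. The fifth is a related gap. The match key is term plus onset date/time, yet the CRF text field takes a date and/or a time. The missing time that triggers the default may therefore also defeat the override.

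**Step 2. Does 9.1.4 govern the IRR count?** SAP 9.1.5 does not cite 9.1.4. It uses the Category 1 window almost unchanged, and 9.1.4 is the only section that turns that window into rules. Applying the default to IRRs is therefore an inference, though the natural one. If it is wrong, IRRs have no rule for a missing onset time at all.

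**Step 3. Can the count be recovered elsewhere?** Tables 14.3.1.7 and 14.3.1.8 show TEAEs by time category. The title of the second is "Number of TEAEs by MedDRA System Organ Class / Preferred Term by Time Categories for Overall", which shows no split by relatedness. Table 14.3.1.5 gives relatedness without timing. No planned table crosses the two for untimed events. Listings 9.2 and 9.4 would allow a review by hand.

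**Step 4. Size.** Inputs: 22 planned patients (Protocol 10.1), all assumed treated, and m patients whose only IRR is displaced (m is assumed; the documents give no figure).

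Drop in the share of patients with an IRR = m/22:
- m = 1: 1/22 = 4.5 points
- m = 2: 2/22 = 9.1 points
- m = 3: 3/22 = 13.6 points

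The patient-level IRR tables are also split by gender. Women are at most 25% of treated patients: 0.25 × 22 = 5.5, so at most 5. One displaced woman moves that subgroup by at least 1/5 = 20 points.

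In the IRR category summary, percentages use the total number of IRRs as denominator. Losing an event there lowers the count, but it can move an individual percentage either way.

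**The case against.** **The rule is a disclosed convention.** This is correct. SAP 9.1.4 announces that it covers missing dates and times, and 9.1.3 limits its worst-case list to named fields. A reader might infer that the two sections contradict each other, but the documents do not support that. They differ in direction, and the plan does not show what the difference does to the IRR count.

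**Untimed events probably arose later.** Patients are observed for two hours after dosing, with repeated vital signs, so events inside the window are the ones most likely to be seen and timed. This is a fair argument for the main rule. It weakens once observation is cut to one hour (Protocol 7.4) or infusions move to the home. Absence from the Drug Administration CRF does not settle it either, because that form also asks about events up to 24 hours.

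**The statistic may not be shown.** SAP 9.1.5 plans patients with IRRs by system organ class and preferred term. It does not explicitly name an overall any-IRR row, and the table shells are in a separate document. The 4.5 points apply to whichever patient-level row loses a patient.

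**Restarted infusions.** Protocol Appendix 3 has the infusion stopped at the first sign of a reaction. If the symptoms resolve and were not progressive or severe, "then administration of the drug may continue according to the algorithm provided above, and at the discretion of the Investigator and Medical Director". A reader might infer that a paused and resumed infusion has no defined end for the 2-hour clock, because the operative rules in 9.1.4 refer to a stop. That does not hold. The IRR definition and every category label count from completion, which for a resumed infusion means the final stop. This is a wording mismatch and no more.

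**Conclusion.** The point holds as a minor one. On the natural reading of SAP 9.1.4 and 9.1.5 together, a related infusion-day TEAE with no onset time and no usable CRF record is not counted as an IRR. Relative to the alternative, this can only lower the IRR count.

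The size is unknown. Each patient whose only IRR is displaced is 4.5 percentage points of 22, and if there are no such patients nothing changes. The conclusion assumes that 9.1.4 governs IRR timing and that some related infusion-day events lack both a time and a usable match.

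A reader might go further and infer that IRRs are in fact under-reported. The documents do not support that: they give no frequency, the events remain in the TEAE tables and listings, and some of them will truly have begun after two hours. The summaries are descriptive, so no test is affected.

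**What to change.** Keep the main rule and add to SAP 9.1.5:

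> A worst-case row, shown beside the main IRR count, will also include every related TEAE dated on an infusion day that has no onset time and no usable Drug Administration CRF record. Injection site reactions are excluded as listed above.

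Add to SAP 9.1.4:

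> Where the onset time is missing, a match on event term and onset date is sufficient for the Drug Administration CRF category to apply.

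The main row and the worst-case row then bracket the answer for these events. If none exist, the two rows agree and the main count is confirmed.

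As an optional clean-up, replace the reference to the stop in the 9.1.4 operative rules with completion (final stop), in line with the labels.

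The cost is two sentences and one extra row in the IRR tables, from data already collected, with no protocol change. The downside is a possibly less favourable IRR figure beside the main one. SAP 7.5 says this SAP covers the final analyses, including new ones, so the row fits there. Otherwise SAP 2 allows it through a change request or note to file.

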9.1.5. Infusion Related Reactions (IRR)

The IRRs are those treatment emergent adverse events (TEAE) which occurred during the infusion or within 2 hours after the completion of the infusion and the causality of the adverse events are determined to be definitely, probably, or possibly related, based on the the site reports in the eCRF.

Injection site reactions which are not considered IRR are excluded from the summary of IRRs, and will be identified based on their SOC and PT, as listed in the following table:

MedDRA SOC	MedDRA Preferred Term
General disorders and administration site conditions	Infusion site discomfort
	Injection site discomfort
	Infusion site pain
	Injection site pain
	Infusion site hematoma
	Injection site hematoma
Injury poisoning and procedural complications	Contusion
	Procedural site reaction
	Procedural pain
Vascular disorders	Vein rupture

The number and percentage of IRRs in the following categories will be summarized for overall, and by gender, FD Classification, and Treatment Emergent pegunigalsidase alfa ADA. The percentage will be based on the total number of IRRs of the population or subset. In addition, the number and percentage of IRR will be summarized by administration location (Home/Site). The summary will include the

following categories:

- Overall number of IRR (used to calculate the percentage),
- Mild or Moderate IRR,
- Severe IRRs,
- Very Severe IRRs,
- Serious IRR.
- IRR that lead to study discontinuation
- IRR that lead to death

Number and percentage of patients with IRRs by MedDRA SOC and PT will be summarized for overall, and by gender, FD Classification, and Treatment Emergent ADA. The number and percentage of patients with IRRs by MedDRA SOC and PT and severity will be summarized for overall.

Number of IRRs by MedDRA SOC and PT will be summarized for overall, and by gender, FD Classification, and Treatment Emergent pegunigalsidase alfa ADA. The number of IRRs by MedDRA SOC and PT and severity will be summarized as well for overall.

9.2. Clinical Laboratory Test Results

The laboratory test results will be summarized, for overall and by gender, by descriptive statistics at the scheduled visits, including the change from baseline and percent change from baseline for continuous results. For the continuous test results being classified into the three categories (low, normal, high) according to the normal ranges, the shift table from baseline to each post-baseline visit will be presented as well. When available, all the test results in the following table will be summarized.

Hematology:	Biochemistry:
Hemoglobin	Alanine transaminase
Platelets	Albumin
Total white blood cell count	Alkaline phosphatase
	Aspartate transaminase
Coagulation Profile:	Bilirubin (total)
Partial thromboplastin time (PTT)	Blood urea nitrogen
Prothrombin time (PrT)	Calcium

	Creatinine
Vitamin D	Creatine phosphokinase
	Cystatin c
Urinalysis:	Gamma-glutamyl transferase
Dipstick for presence of Blood	Glucose
Dipstick for presence of Glucose	Lactate dehydrogenase
Dipstick for presence of Ketones	Phosphate (inorganic)
Dipstick for presence of Protein	Potassium
	Sodium
	Total protein
	Uric acid

Note to programmers:

- Values in urinalysis (e.g. protein), spot urine test (protein to creatinine ratio UPCR), and chemistry (e.g. bilirubin) started with a '<' sign will be excluded from the analysis, but will be presented in listings with the '<' sign.
- Serum creatinine can be recorded in two units, µmol/L and mg/dL. In calculation of eGFR or summary of creatinine, the value in µmol/L needs to be converted to mg/dL using the following conversion formula: 1 mg/dL = 88.4 µmol/L.
- Serum creatinine can be entered in two fields in the SDTM (CHEMISTRY and ENZYME). When the results from same sample is entered at both fields, then the value is identical. In such cases, only one of them will be taken in the analysis.

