8.3 Adverse Events

8.3.1 Adverse Events (AE) and Serious Adverse Events (SAE)

An adverse event (AE) is any untoward medical occurrence in a subject participating in a clinical trial. An adverse event can be any unfavorable and unintended sign, symptom or disease temporally associated with the use of the study medication, whether or not considered related to the study medication. AEs will be collected from the start of treatment until 30 days following the final visit dose. Any events occurring prior to treatment will be recorded on the medical history page with the event name and onset date and end date if not continuing. Pre-existing, known clinically significant conditions observed at screening should be recorded as medical history.

This definition also includes accidental injuries, reasons for any change in medication (drug and/or dose) other than planned titration, reasons for admission to a hospital, or reasons for surgical procedures (unless for minor elective surgery for a pre-existing condition). It also includes adverse events commonly observed and adverse events anticipated based on the pharmacological effect of the study medication. Any laboratory abnormality assessed as clinically significant by the Investigator must be recorded as an adverse event.

A treatment emergent adverse event is any adverse event occurring after start of study medication and within the time of residual drug effect, or a pre-treatment adverse event or pre-existing medical condition that worsens in intensity after start of study medication and within the time of residual drug effect.

Adverse events should be recorded as diagnoses, if available. If not, separate sign(s) and symptom(s) are recorded. One diagnosis/symptom should be entered per record.

Note that death is not an event, but the cause of death is. An exception is the event of sudden death of unknown cause. Note that hospitalization is not an event; however, the reason for hospitalization is. Procedures are not events; the reasons for conducting the procedures are. In general, only the reason for conducting the procedure will be captured as an adverse event. However, if deemed necessary by the Investigator, a procedure can be captured along with the reason for conducting the procedure.

An overdose or medication error is not an adverse event unless it is temporally associated with an unfavourable or unintended sign or symptom.

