10.4.2 Clinical Laboratory

Summary statistics of all central and local laboratory test results (biochemistry, hematology, and urinalysis) will be presented for each visit. The change from baseline (Visit 1) to each post-treatment visit will also be presented.

If the test results were classified (e.g., low, normal, high), the frequency count and percentage will be presented for each visit, and shift table from baseline will be provided as well.

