9.6. Treatment-emergent Anti-Pegunigalsidase alfa Antibodies

Treatment emergent anti-pegunigalsidase alfa antibodies (ADA+ vs. ADA-) is defined in Section 7.4.

The number and percentage of patients who are Treatment emergent ADA will be summarized by visit

An overall anti-pegunigalsidase alfa antibodies status per patient during the study (“positive” if positive at any visit, negative if negative at all visits), will be summarized as well.

Analyses will be repeated by gender and by Fabry disease classification (classic/non-classic).

Note to programmer: The treatment-emergent anti-pegunigalsidase alfa antibodies (ADA) including the three test results:

- a. IgG = negative if ‘IgG Screening (Presumptive Pos/Neg)’ (LBTEST) for LBSCAT = for PRX-102 is Negative; otherwise the status will be determined based on the result of ‘IgG Immunodepletion (Pos/Neg)’ : Positive or Negative,
- b. Neutralizing Antibody = the result of ‘Neutralizing Antibody (Pos/Neg)’ (LBTEST): Positive or Negative,
- c. IgE = the result of ‘IgE Screening (Presumptive Pos/Neg)’ (LBTEST): Positive or Negative.

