14.3.1.10.2	Number of IRRs by MedDRA System Organ Class / Preferred Term by Baseline FD Classification and Treatment Emergent ADA	Safety
14.3.1.11	Number of IRRs by MedDRA System Organ Class / Preferred Term and Severity for Overall	Safety
14.3.1.12.1	Number of Subjects with IRRs by MedDRA System Organ Class / Preferred Term for Overall and by Gender	Safety

Number	Title	Population
14.3.1.12.2	Number of Subjects with IRRs by MedDRA System Organ Class / Preferred Term by Baseline FD Classification and	Safety
14.3.1.13	Number of Subjects with IRRs by MedDRA System Organ Class / Preferred Term and Severity for Overall	Safety
14.3.1.14	Treatment-Emergent Adverse Events Leading to Withdrawal or Death	Safety
14.3.1.15.1	Number of Subjects with Injection Site Reaction TEAE for Overall and by Gender	Safety
14.3.1.15.2	Number of Subjects with Injection Site Reaction TEAE by Baseline FD Classification and Treatment Emergent ADA	Safety
14.3.1.16.1	Number of Injection Site Reactions TEAE for Overall and by Gender	Safety
14.3.1.16.2	Number of Injection Site Reactions TEAE by Baseline FD Classification and Treatment Emergent ADA	Safety
14.3.1.17	Number of Subjects with Serious TEAE by MedDRA System Organ Class / Preferred Term for Overall and by Gender	Safety
14.3.1.18	Number of Subjects with Serious TEAE by MedDRA System Organ Class / Preferred Term and Relationship to Study Drug for Overall	Safety

Safety – Laboratory Test Results:

Number	Title	Population
14.3.4.1.1	Laboratory Test Results – Biochemistry for Overall and by Gender	Safety
14.3.4.1.2	Laboratory Test Results Shift from Baseline – Biochemistry for Overall and by Gender	Safety
14.3.4.2.1	Laboratory Test Results – Hematology for Overall and by Gender	Safety
14.3.4.2.2	Laboratory Test Results Shift from Baseline – Hematology for Overall and by Gender	Safety
14.3.4.3	Laboratory Test Results – Urinalysis for Overall and by Gender	Safety
14.3.4.4	Laboratory Test Results – Coagulation Profile at Screening for Overall and by Gender	Safety
14.3.4.5	Laboratory Test Results – Vitamin D at Screening for Overall and by Gender	Safety
14.3.4.6	Anti-PRX-102 Antibodies for Overall and by Gender and Baseline FD Classification	Safety

Safety – Other:

Number	Title	Population
14.3.5.1	Vital Signs for Overall and by Gender	Safety
14.3.5.2.1	Physical Examinations for Overall and by Gender	Safety
14.3.5.2.2	Physical Examinations – Shift from Baseline for Overall and by Gender	Safety

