12. TABLE SHELLS

The table shells are to be provided in a separate document.

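### The by-visit laboratory tables cannot show how many patients were ever abnormal on treatment; add one shift to the worst post-baseline value

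*SAP*

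**What the plan says.** Safety is the primary objective (Protocol 5.1, SAP 3.1), and clinical laboratory tests come first among the safety endpoints in SAP 3.2.1.

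SAP 9.2 plans two kinds of laboratory table. For the summaries, "The laboratory test results will be summarized, for overall and by gender, by descriptive statistics at the scheduled visits". For continuous results classed as low, normal or high, "the shift table from baseline to each post-baseline visit will be presented as well". Protocol 10.4.2 is built the same way: for classified results, "the frequency count and percentage will be presented for each visit, and shift table from baseline will be provided as well".

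The index in SAP 11.1 carries this through. Table 14.3.4.1.2 is "Laboratory Test Results Shift from Baseline – Biochemistry for Overall and by Gender", and Table 14.3.4.2.2 is its haematology counterpart. No laboratory table in the index uses a worst post-baseline value or counts patients abnormal at any time under the tests of SAP 9.2. Neither document gives a rule for unscheduled laboratory results. The layout cannot be checked, because SAP 12 says: "The table shells are to be provided in a separate document".

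There is a second route to a table. Under Protocol 8.3.1, "Any laboratory abnormality assessed as clinically significant by the Investigator must be recorded as an adverse event".

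**The concern.** A safety reader wants to know how many of the 22 patients became abnormal on treatment, analyte by analyte. A by-visit shift table answers a different question: how many were abnormal at this visit. The rows cannot be added, because the same patient may appear in several of them. Nor do they show the overlap. Low counts at every visit may therefore come from one persistently abnormal patient or from several patients affected once each.

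A second, smaller gap concerns any result from an unscheduled sample. It has no place in a summary restricted to scheduled visits. The adverse event tables pick it up only if the investigator judges it clinically significant, and then as an event term rather than a laboratory value.

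At stake is how one listed safety endpoint is presented. No estimate, sample size or decision rule is affected.

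**Working it through.** The plan states no figure that depends on this point. SAP 4.1 says that 22 patients were chosen without a formal calculation, so there is nothing to reproduce. The check is whether by-visit counts determine the number ever abnormal.

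**Inputs**
- N = 22 planned patients (SAP 4.1; Protocol 10.1).
- Post-baseline haematology and full biochemistry: Visits 7, 14, 20 and 27, so V = 4 (flow charts in Protocol 9 and SAP 4.2). With infusions every two weeks, Visit n falls at week 2(n − 1), which gives weeks 12, 26, 38 and 52.
- Post-baseline creatinine and cystatin C: Visits 3, 5, 7, 9, 11, 14, 16, 18, 20, 22, 24 and 27, so V = 12 (same flow charts).
- k = number of patients abnormal at each visit. This is assumed, because the documents give no rates. All 22 patients are taken to have a result at every visit.

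**Formula.** If k patients are abnormal at each of V visits, the number ever abnormal is smallest when they are always the same patients (k) and largest when they are all different (the lesser of N and V × k).

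| Tests | k per visit | Each row shows | Fewest ever abnormal | Most ever abnormal |
|---|---|---|---|---|
| Haematology, biochemistry (V = 4) | 1 | 1/22 = 4.5% | 1 (4.5%) | 4 × 1 = 4 (18.2%) |
| Haematology, biochemistry (V = 4) | 2 | 2/22 = 9.1% | 2 (9.1%) | 4 × 2 = 8 (36.4%) |
| Haematology, biochemistry (V = 4) | 3 | 3/22 = 13.6% | 3 (13.6%) | 4 × 3 = 12 (54.5%) |
| Creatinine (V = 12) | 1 | 1/22 = 4.5% | 1 (4.5%) | 12 × 1 = 12 (54.5%) |
| Creatinine (V = 12) | 2 | 2/22 = 9.1% | 2 (9.1%) | min(22, 24) = 22 (100%) |

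Identical rows are therefore compatible with widely different numbers of patients, before any unscheduled sample is considered.

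**Where in the range.** This depends on persistence within a patient. For k = 1 and V = 4, full persistence gives 1/22 = 4.5%. Independence across visits gives 1 − (21/22)^4 = 17.0%, or 22 × 0.170 = 3.7 patients. Independence is unlikely for chronic organ disease, so 17.0% is an illustration and not an expected value.

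**Unscheduled results.** In SAP 9.2 the restriction to scheduled visits is attached to the descriptive statistics. The shift sentence speaks only of post-baseline visits. Exclusion is thus explicit for the first and only the natural reading for the second.

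**What the plan does elsewhere.** For adverse events, SAP 9.1.3 takes each patient's most extreme severity and relationship. For antibodies, SAP 9.6 gives each patient an overall status, positive "if positive at any visit, negative if negative at all visits". The routine laboratory tests have no such per-patient summary.

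**The case against.** The strongest reply is that little is hidden.
- **Listings.** SAP 11.3 plans listings of biochemistry, haematology and urinalysis, or relies on equivalent raw-data listings. With 22 patients these can be read one by one.
- **Kidney function.** Creatinine is drawn at 12 post-baseline visits, and SAP 10.1.3 shows eGFR at all visits per patient (Table 14.2.1.2). Protocol 8.3.3 makes a 1.5-fold creatinine rise from the previous value, with investigator assessment, an adverse event.
- **Adverse events.** Clinically significant abnormalities reach tables that count patients at any time.
- **Consistency.** The SAP follows Protocol 10.4.2, so there is no contradiction.
- **Bias of the alternative.** The worst of four values is set against one baseline value in a study with no comparator. A purely random 5% rate per visit, independent across visits, becomes 1 − 0.95^4 = 18.5% ever abnormal with no drug effect.

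All of this stands as a limit on the point, and the last item must be stated in the table label. It does not supply the missing count. Listings leave the reader to count by hand without a pre-stated rule, and the adverse event route depends on the investigator's judgement in an open-label study.

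A reader might go further and infer that unscheduled worst values enter no table at all, or that toxicity between visits is being missed. The documents do not support that. The shift sentence does not state the exclusion, and the shells are not available. Neither document describes unscheduled haematology or biochemistry draws, so their number is unknown. Significant abnormalities do reach the adverse event tables. Samples at premature withdrawal are already the Visit 27 assessments (Protocol 9.1.9). No table can recover a result that was never drawn.

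**Conclusion.** The point holds as a gap in tabulation. The planned laboratory tables cannot give the number of distinct patients ever abnormal. For haematology and biochemistry, one abnormal patient per visit leaves 1 to 4 of 22 possible (4.5% to 18.2%), and two per visit leave 2 to 8 (9.1% to 36.4%). The top of each range requires different patients at every visit and should not be quoted alone.

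The conclusion rests on the table index, since the shells are in a separate document, and on assumed per-visit counts with complete data. The part about unscheduled results is secondary: certain for the descriptive statistics, inferred for the shift tables, and of unknown size. The change is worth making because it is cheap and concerns a listed safety endpoint under the primary objective. It does not correct an error.

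**What to change.** Add to SAP 9.2 and to Tables 14.3.4.1.2 and 14.3.4.2.2, for each analyte:
- one shift from baseline to the worst post-baseline value per patient, with lowest and highest handled separately;
- the number and percentage of patients ever abnormal after baseline;
- a statement that all post-baseline samples count: scheduled, unscheduled and withdrawal.

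Keep the by-visit tables for means and trends.

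Label the new rows as descriptive. The label should say that the worst of several values is compared with a single baseline value, that there is no comparator, and that normal fluctuation and more frequent testing raise the percentage, so it is not evidence of a drug effect by itself.

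The cost is a little programming on data already collected. Sample size and the eGFR slope comparison are unchanged. SAP 7.5 already provides for new analyses at the final stage; this one should be recorded as added after the interim analysis.
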